9.4 Payments and Reimbursement of Human Research Subjects

Trial participants will not be paid for participation in the trial. Trial participants will be reimbursed for expenses that are incurred due to participation in the trial. These expenses may include but are not limited to: transportation costs, child care costs, costs of missed wages due to trial related activities, clinic appointments and other expenses at the discretion of the principal investigator and site IRB/IEC. The amounts and payment schedules for payment shall be determined by the principal investigator and the IRB/IEC at each site.

10 STUDY COMPLETION

At the discretion of the sponsor, all materials and supplies provided to the investigator will be returned or disposed of in compliance with local regulatory requirements upon authorization from the sponsor, upon study completion. The investigator or designated clinical site staff will notify the IRB/IEC when the study has been completed.

11 PUBLICATIONS

The final study report will be made available to the principal investigator(s) for purposes of publications. The principal investigator and study staff must send all manuscripts, abstracts, and presentations using data from this study to the sponsor for review prior to their submission. The sponsor reserves the right to delete any part or parts of such materials deemed to be confidential or proprietary. From the sponsor. All changes to the protocol must be submitted to the IRB/IEC and must be approved by the IRB/IEC unless they are administrative changes, typographical errors or required for subject safety prior to their implementation. This is the third version of the protocol.

12 CHANGES IN THE CURRENT VERSION OF THE PROTOCOL

The changes to Version 6.0 of the protocol are listed in Table 12-1. Version 5.0 was never submitted to any clinical site but was used in discussions with the US FDA thus the last clinical protocol was Version 4.0. Minor grammatical or orthographic changes may not be listed. The major changes to the protocol are:

- The operation of the DSMB to permit enrollment of the NRG is revised to recognize that all subjects need not have a RVNA ≥ 0.5 IU/mL.

Table 12-1 Table of Changes for Version 6.0 of Protocol

Section Modified	Version 4.0	Version 6.0	Page
3.4.1 Blinding at the Study Level	The LRG and the NRG are both blinded until Study Day 365. If the last subject in LRG reaches Study Day 365 even if the NRG is still in progress, then the LRG group may be unblinded	The LRG and the NRG are both blinded until Study Day 365. If the last subject in LRG reaches Study Day 365 even if the NRG is still in progress, then the LRG group may be unblinded. The LRG may be unblinded to the extent recommended or	49

Section Modified	Version 4.0	Version 6.0	Page
		required by the DSMB for analysis of safety or efficacy data for Study Day 99 DSMB review.	
4.4 Study Rabies Vaccine in Philippines	Study rabies vaccine in Philippines and Thailand	Study rabies vaccine in Philippines	62
5.1.5.3 DSMB Review of Safety and Pharmacodynamic Activity in the Initial and General Enrollment LRG	
The sponsor will collect blinded RVNA results and adverse events through Study Day 99 from all subjects in the LRG General and Initial enrollment groups and provide them to the DSMB.
 
Permission to enroll the General Enrollment of the NRG may be granted at Study Day 183 if
 
 • no protocol stopping rules are met (Section 6.3) and if • no severe related adverse events other than local injection site manifestations are encountered due to SYN023 in the initial and general enrollment of the LRG • The RVNA values are all in the protective range in SYN023 recipients Study Days 8 through 99 (Section 3.9.2). 	
The sponsor will collect blinded RVNA results and adverse events through Study Day 99 from all subjects in the LRG General and Initial enrollment groups and provide them to the DSMB.
 
Permission to enroll the General Enrollment of the NRG may be granted at Study Day 183 if
 
 • no protocol stopping rules are met (Section 6.3) and if • no severe related adverse events other than local injection site manifestations are encountered due to SYN023 in the initial and general enrollment of the LRG • The RVNA values are in the protective range in $\geq 75\%$ of SYN023 recipients on Study Day 99 (Section 3.9.2). 	65-66
5.1.5.4 DSMB Review of Safety in the NRG	The DSMB will assess the safety after 80 subjects have completed Study Day 99. If	The DSMB will assess the safety (while enrollment continues) after 80 subjects	66

Section Modified	Version 4.0	Version 6.0	Page
	there are no adverse events or patterns of concern	have completed Study Day 99. If there are no adverse events or patterns of concern it will issue permission for the trial to continue.	

APPENDIX B Toxicity Table

Note: From final US FDA guidance: Toxicity Grading Scale for Healthy Adult and Adolescent Subjects Enrolled in Preventive Drug Clinical Trials (September 2007); laboratory values are in conventional and SI units. The laboratory values provided in the tables serve as guidelines and are dependent upon institutional normal parameters. Institutional normal reference ranges should be provided to demonstrate that they are appropriate.

Local Site of Infusion Symptoms	Mild (Grade 1)	Moderate (Grade 2)	Severe (Grade 3)	Very Severe (Grade 4)
Pain	Does not interfere with activity	Repeated use of non-narcotic pain reliever > 24 hours or interferes with activity	Any use of narcotic pain reliever or prevents daily activity	ER visit or hospitalization
Tenderness	Mild discomfort to touch	Discomfort with movement	Significant discomfort at rest	ER visit or hospitalization
Erythema/Redness *	2.5 - 5 cm	5.1 - 10 cm	>10 cm	Necrosis or exfoliative dermatitis
Induration/Swelling **	2.5 - 5 cm and does not interfere with activity	5.1 - 10 cm or interferes with activity	>10 cm or prevents daily activity	Necrosis

8. * In addition to grading the local reaction at the greatest single diameter, the measurement should be recorded as a continuous variable.
 9. ** Induration/Swelling should be evaluated and graded using the functional scale as well as the actual measurement.

Vital Signs*	Mild (Grade 1)	Moderate (Grade 2)	Severe (Grade 3)	Very Severe (Grade 4)
Fever**	38.0 – 38.4°C 100.4 – 101.1°F	38.5 – 38.9°C 101.2 – 102.0°F	39.0 - 40°C 102.1 - 104°F	>40°C >104°F
Tachycardia – beats per minute	101 – 115	116 – 130	>130	ER visit or hospitalization for arrhythmia
Bradycardia – beats per minute	50 – 54	45 – 49	<45	ER visit or hospitalization for arrhythmia
Hypertension (systolic) – mm Hg	141 – 150	151 – 155	>155	ER visit or hospitalization for malignant hypertension
Hypertension (diastolic) – mm Hg	91 – 95	96 – 100	>100	ER visit or hospitalization for malignant hypertension
Hypotension (systolic) – mm Hg	85 – 89	80 – 84	<80	ER visit or hospitalization for hypotensive shock
Respiratory rate – breaths per minute	17 – 20	21 – 25	>25	Intubation

10. * Subject should be at rest for all vital sign measurements. ** Oral temperature; no recent hot or cold beverages or smoking.

Systemic (General)	Mild (Grade 1)	Moderate (Grade 2)	Severe (Grade 3)	Very Severe (Grade 4)
Nausea/vomiting	No interference with activity or 1 - 2 episodes/24 hours	Some interference with activity or >2 episodes/24 hours	Prevents daily activity, requires outpatient IV hydration	ER visit or hospitalization for hypotensive shock
Diarrhea	2 - 3 loose stools or < 400 grams/24 hours	4 - 5 stools or 400 - 800 grams/24 hours	6 or more watery stools or > 800 grams/24 hours or requires outpatient IV hydration	ER visit or hospitalization for hypotensive shock
Headache	No interference with activity	Repeated use of non-narcotic pain reliever > 24 hours or some interference with activity	Significant; any use of narcotic pain reliever or prevents daily activity	ER visit or hospitalization
Fatigue	No interference with activity	Some interference with activity	Significant; prevents daily activity	ER visit or hospitalization

Myalgia	No interference with activity	Some interference with activity	Significant; prevents daily activity	ER visit or hospitalization
Infusion reaction	Requires no intervention and transient in duration	Requires slowing of infusion or non-prescription drug treatment	Requires prescription drug treatment presence of respiratory symptoms	ER visit or hospitalization
Illness or clinical adverse event (as defined according to applicable regulations)	No interference with activity	Some interference with activity not requiring medical intervention	Prevents daily activity and requires medical intervention	ER visit or hospitalization

Serum	Mild (Grade 1)	Moderate (Grade 2)	Severe (Grade 3)	Very Severe (Grade 4)**
Sodium – hyponatremia mEq/L or mmol/L:	132 – 134	130 – 131	125 – 129	<125
Sodium – hypernatremia mEq/L or mmol/L:	144 – 145	146 – 147	148 – 150	>150
Potassium – hyperkalemia mEq/L or mmol/L:	5.1 – 5.2	5.3 – 5.4	5.5 – 5.6	>5.6
Potassium – hypokalemia mEq/L or mmol/L:	3.5 – 3.6	3.3 – 3.4	3.1 – 3.2	<3.1
Glucose – hypoglycemia mg/dL: mmol/L:	65 – 69 3.6 – 3.8	55 – 64 3.0 – 3.5	45 – 54 2.5 – 2.9	<45 <2.5
Glucose – hyperglycemia Fasting - mg/dL: mmol/L: Random – mg/dL: mmol/L:	100 – 110 5.5 – 6.0 110 – 125 6.1 – 6.8	111 – 125 6.1 – 6.8 126 – 200 6.9 – 11.0	>125 >6.8 >200 >11.0	Insulin requirement or hyperosmolar coma
Blood urea nitrogen (BUN) – mg/dL: mmol/L:	23 – 26 8.3 – 9.5	27 – 31 9.6 – 11.2	>31 >11.2	Requires dialysis
Creatinine – elevated mg/dL: umol/L:	1.5 – 1.7 121 – 145	1.8 – 2.0 146 – 170	2.1 – 2.5 171 – 208	>2.5 or requires dialysis >208 or requires dialysis
Calcium – hypocalcemia mg/dL: mmol/L:	8.0 – 8.4 2.00 – 2.10	7.5 – 7.9 1.87 – 1.99	7.0 – 7.4 1.75 – 1.86	<7.0 <1.75
Calcium – hypercalcemia mg/dL: mmol/L:	10.5 – 11.0 2.63 – 2.76	11.1 – 11.5 2.77 – 2.88	11.6 – 12.0 2.89 – 3.00	>12.0 >3.00
Magnesium – hypomagnesemia mg/dL: mmol/L:	1.3 – 1.5 0.52 – 0.62	1.1 – 1.2 0.43 – 0.51	0.9 – 1.0 0.37 – 0.42	<0.9 <0.37
Phosphorus – hypophosphatemia mg/dL: mmol/L:	2.3 – 2.5 0.73 – 0.80	2.0 – 2.2 0.63 – 0.72	1.6 – 1.9 0.51 – 0.62	<1.6 <0.51
CPK – elevated mg/dL or ukat/L:	1.25 – 1.5 x ULN***	1.6 – 3.0 x ULN	3.1 – 10 x ULN	>10 x ULN
Albumin – hypoalbuminemia g/dL: g/L:	2.8 – 3.1 28 – 31	2.5 – 2.7 25 – 27	<2.5 <25	----
Total protein – hypoproteinemia g/dL: g/L:	5.5 – 6.0 55 – 60	5.0 – 5.4 50 – 54	<5.0 <50	----
Alkaline phosphatase (ALP) – increased	1.1 – 2.0 x ULN	2.1 – 3.0 x ULN	3.1 – 10 x ULN	>10 x ULN
Liver Function Tests (LFT): AST, ALT – increased	1.1 – 2.5 x ULN	2.6 – 5.0 x ULN	5.1 – 10 x ULN	>10 x ULN
Bilirubin (with any increase in LFT) - increased	1.1 – 1.25 x ULN	1.26 – 1.5 x ULN	1.51 – 1.75 x ULN	>1.75 x ULN

CONFIDENTIAL

Bilirubin (with normal LFT) - increased	1.1 – 1.5 x ULN	1.6 – 2.0 x ULN	2.1 – 3.0 – x ULN	>3.0 x ULN
Cholesterol – increased mg/dL: mmol/L:	201 - 210 6.0 – 6.3	211 – 225 6.4 – 6.7	>226 >6.7	---- ----
Pancreatic enzymes: amylase, lipase – increased	1.1 – 1.5 x ULN	1.6 – 2.0 x ULN	2.1 – 5.0 x ULN	>5.0 x ULN

11. ** The clinical signs or symptoms associated with laboratory abnormalities might result in characterization of the laboratory abnormalities as Very Severe (Grade 4). For example, a low sodium value that falls within a grade 3 parameter (125-129 mEq/L) should be recorded as a Grade 4 hyponatremia event if the subject had a new seizure associated with the low sodium value.

12. *** ULN (upper limit of normal) dependent on normal reference ranges per institutional parameters.

Hematology	Mild (Grade 1)	Moderate (Grade 2)	Severe (Grade 3)	Very Severe (Grade 4)
Hemoglobin (Female) – g/dL: g/L:	11.0 – 12.0 110 – 120	9.5 – 10.9 95 – 109	8.0 – 9.4 80 – 94	<8.0 <80
Hemoglobin (Male) – g/dL: g/L:	12.5 – 13.5 125 – 135	10.5 – 12.4 105 – 124	8.5 – 10.4 85 – 104	<8.5 <85
WBC – increased cells/mm ³ : cells x 10 ⁹ /L:	10,800 – 15,000 10.8 – 15.0	15,001 – 20,000 15.1 – 20.0	20,001 – 25,000 20.1 – 25.0	>25,000 >25.0
WBC – decreased cells/mm ³ : cells x 10 ⁹ /L:	2,500 – 3,500 2.5 – 3.5	1,500 – 2,499 1.5 – 2.4	1,000 – 1,499 1.0 – 1.4	<1,000 <1.0
Lymphocytes – decreased cells/mm ³ : cells x 10 ⁹ /L:	750 – 1,000 0.8 – 1.0	500 – 749 0.5 – 0.7	250 – 499 0.3 – 0.4	<250 <0.3
Neutrophils – decreased cells/mm ³ : cells x 10 ⁹ /L:	1,500 – 2,000 1.5 – 2.0	1,000 – 1,499 1.0 – 1.4	500 – 999 0.5 – 0.9	<500 <0.5
Eosinophils – increased cells/mm ³ : cells x 10 ⁹ /L:	650 – 1,500 0.7 – 1.4	1,501 – 5,000 1.5 – 5.0	>5,000 >5.0	Hypereosinophilic
Platelets – decreased cells/mm ³ : cells x 10 ⁹ /L:	125,000 – 140,000 125 – 140	100,000 – 124,000 100 – 124	25,000 – 99,000 25 – 99	<25,000 <25
International normalized ratio (INR) – increased	>1.0 – 1.10 x ULN**	1.11 – 1.20 x ULN	1.21 – 1.25 x ULN	>1.25 x ULN
Partial thromboplastin time (PTT) – increased	>1.0 – 1.2 x ULN	1.21 – 1.4 x ULN	1.41 – 1.5 x ULN	>1.5 x ULN
Fibrinogen – increased mg/dL: g/L:	400 – 500 4.00 – 5.00	501 – 600 5.01 – 6.00	>600 >6.00	---- ----
Fibrinogen – decreased mg/dL: g/L:	150 – 200 1.50 – 2.00	125 – 149 1.25 – 1.49	100 – 124 1.00 – 1.24	<1.0 or associated with gross bleeding or disseminated intravascular coagulation (DIC)

13. ** “ULN” is the upper limit of the normal range.

Urine	Mild (Grade 1)	Moderate (Grade 2)	Severe (Grade 3)	Very Severe (Grade 4)
Protein	Trace	1+	2+	Hospitalization or dialysis
Glucose	Trace	1+	2+	Hospitalization for hyperglycemia
Blood (microscopic) – red blood cells per high power field (rbc/hpf)	1 – 10	11 – 50	>50 and/or gross blood	Hospitalization or packed red blood cells (PRBC) transfusion

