3.12.3 Clinical Assessments and Laboratory Tests

Abnormal results and findings will be discussed with the subject, or the subject will be referred for follow-up with their healthcare provider if necessary.

Results from clinical laboratory tests obtained on the study must be reviewed by the investigator (or a designee who is a medically qualified study team member) within 72 hours of receiving the results to determine if abnormalities exist. If the laboratory value is abnormal and has increased in toxicity grade (see Appendix B for toxicity grading scales) from pre-vaccination values, it must be reported as an adverse event and repeated promptly to demonstrate resolution.

Additional laboratory tests may be performed if the investigator deems them to be necessary to fully evaluate an adverse event. In the event that the investigator elects to order non-protocol-specified laboratory tests, the investigator must record the rationale for the tests and a

determination of clinical significance of the result in the source documents. The investigator must keep the medical monitor informed of adverse events of clinical significance.

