5.1.5.2 DSMB Evaluation of Safety and Pharmacodynamic Activity in the Initial Enrollment LRG

The sponsor will collect blinded RVNA results and adverse events through Study Day 29 from the subjects in the LRG initial enrollment group and provide this information to the DSMB. Permission to enroll the General Enrollment of the LRG may be granted if

- no protocol stopping rules are met (Section 6.3) and if
- no severe related adverse events other than local injection site manifestations are encountered due to SYN023 in the initial enrollment of the LRG
- the serum RVNA values are all in the protective range (≥ 0.5 IU/mL Section 3.9.2) on Study Days, 8 through 29 in the SYN023 recipients.

The DSMB will issue a written determination permitting enrollment of the general enrollment group of the LRG and inform the sponsor of this determination. It is acknowledged that some HRIG recipients may not have achieved ≥ 0.5 IU/mL RVNA by Study Day 8.

5.1.5.3 DSMB Review of Safety and Pharmacodynamic Activity in the Initial and General Enrollment LRG

The sponsor will collect blinded RVNA results and adverse events through Study Day 99 from all subjects in the LRG General and Initial enrollment groups and provide them to the DSMB. Permission to enroll the General Enrollment of the NRG may be granted at Study Day 183 if

- no protocol stopping rules are met (Section 6.3) and if
- no severe related adverse events other than local injection site manifestations are encountered due to SYN023 in the initial and general enrollment of the LRG
- The RVNA values are in the protective range in $\geq 75\%$ of SYN023 recipients on Study Day 99 (Section 3.9.2).

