5.4 Assessing Severity

The safety concepts of “severity” and “seriousness” are distinct concepts (see Section 5.8). Severity refers to a degree of clinical manifestation. “Seriousness” refers to defined outcomes from an adverse event. A severe adverse event is not always serious and a serious adverse event is not always severe.

For all adverse events, the investigator (or designee, who is a healthcare professional; is someone the investigator deems qualified to review adverse event information, to provide a medical evaluation of the event, and to classify the event based upon medical judgment and the severity categories described below) is responsible for assessing the severity of the event and the causal relationship of the event to the Study Drug.

The **severity** of all adverse events, including clinical findings and abnormal laboratory values, will be classified as one of the following grades:

1. **Mild**
2. **Moderate**
3. **Severe**

A Toxicity Table is provided in the protocol appendices for the assessment of severity of specified adverse events. The Toxicity Table Adverse Event Grades do not correlate directly with the classical severity grades of mild, moderate and severe. FOR THE PURPOSES OF RECORDING EVENTS ON THE CRF, Toxicity Table Grade 1 events will be considered mild in severity, Toxicity Table Grade 2 events will be considered moderate in severity, and both Toxicity Table Grade 3 and 4 events will be considered as severe. In the Toxicity Table certain local reactions such as erythema (redness) and swelling are graded according to size. Laboratory values are graded according to level of deviation from the normal range.

For adverse events not listed in the Toxicity Table determination of severity requires some level of interpretation as outlined below. The degree of incapacity caused by the adverse event and the level of medical intervention required for treatment may be helpful in assessing the overall severity of the adverse event.

For example:

- “Mild” events are generally regarded as noticeable but have no impact on normal activities; they may or may not require over-the-counter treatment managed by the subject.
- “Moderate” events generally have some impact on an individual’s normal activities and may require general symptomatic medical intervention by a healthcare professional or by the subject.

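### In the Appendix B Toxicity Table, the creatinine limits in µmol/L do not equal the mg/dL limits printed for the same grades, so some results near the band edges would be graded one step higher if reported in µmol/L.

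*Protocol*

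**What the plan says.** The introduction to Appendix B says that laboratory values are given in both conventional and SI units. It calls them guidelines that depend on institutional normal parameters. The creatinine row is labelled "Creatinine – elevated mg/dL: umol/L", and its cells read as follows, mg/dL first:

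- Grade 1: "1.5 – 1.7 121 – 145"
- Grade 2: "1.8 – 2.0 146 – 170"
- Grade 3: "2.1 – 2.5 171 – 208"
- Grade 4: ">2.5 or requires dialysis >208 or requires dialysis"

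These limits are used in several places.

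- Creatinine is one of the serum chemistries drawn on Study Days 1, 4, 15 and 43 in both risk groups (Protocol Tables 3-1 and 3-2).
- Protocol 3.12.3 makes a result a reportable adverse event on this condition: "If the laboratory value is abnormal and has increased in toxicity grade".
- Protocol 5.4 records Grade 1 as mild and Grade 2 as moderate, and adds that "both Toxicity Table Grade 3 and 4 events will be considered as severe".
- Protocol 7.7 tabulates newly abnormal or grade-increased values, and SAP 9.2 builds shift tables from Appendix B.
- Protocol 5.1.5.2 makes it a condition of opening general LRG enrollment that "no severe related adverse events other than local injection site manifestations are encountered due to SYN023". Section 5.1.5.3 sets the same condition for opening the NRG.

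Neither document fixes a reporting unit for creatinine or says which scale governs.

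**The concern.** Two sets of limits for one grade should be the same limits in different units. If they are not, the grade depends on the unit that the laboratory happens to print. The trial is to run in at least two countries (Protocol 2.2), and Protocol 3.2.7 allows for more than one clinical laboratory, so mixed units are possible. The consistency of adverse event reporting, recorded severity and shift tables for a scheduled kidney marker is at stake. Protocol 5.18 also names a raised serum creatinine as a late reflection of glomerular damage in immune complex illness.

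**Working it through.** **Inputs.** The printed limits come from the creatinine row of Appendix B. The conversion factor is not in the documents. I assume 88.4 µmol/L per mg/dL, which is 10,000 divided by a molar mass of 113.12 g/mol, and I repeat the check at 88.0.

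**Step 1: convert each limit** (mg/dL × 88.4) and compare it with the printed value.

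| Limit | mg/dL | Converted µmol/L | Printed µmol/L | Difference | Printed ÷ mg/dL |
|---|---|---|---|---|---|
| Grade 1 lower | 1.5 | 132.6 | 121 | −8.7% | 80.7 |
| Grade 1 upper | 1.7 | 150.3 | 145 | −3.5% | 85.3 |
| Grade 2 lower | 1.8 | 159.1 | 146 | −8.2% | 81.1 |
| Grade 2 upper | 2.0 | 176.8 | 170 | −3.8% | 85.0 |
| Grade 3 lower | 2.1 | 185.6 | 171 | −7.9% | 81.4 |
| Grade 3 upper | 2.5 | 221.0 | 208 | −5.9% | 83.2 |

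Grade 4 begins above 221.0 µmol/L by conversion and above 208 as printed. Read the other way, the printed bands are 1.37–1.64, 1.65–1.92, 1.93–2.35 and >2.35 mg/dL.

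**Step 2: can rounding explain it?** The mg/dL bands leave gaps of 0.1, so I also compared cut-points in the middle of the gaps: 120.5/1.45 = 83.1, 145.5/1.75 = 83.1, 170.5/2.05 = 83.2 and 208.5/2.55 = 81.8. None is near 88.4. At a factor of 83.2, every tenth of a mg/dL from 1.2 to 2.7 gets the same grade on both scales. The row is thus nearly self-consistent, but at the wrong factor.

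**Step 3: grade the same result on both scales**, for the 12 values from 1.4 to 2.5 mg/dL in steps of 0.1.

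| mg/dL | µmol/L | Grade by mg/dL | Grade by µmol/L | Recorded severity |
|---|---|---|---|---|
| 1.4 | 123.8 | none | 1 | none v mild |
| 1.7 | 150.3 | 1 | 2 | mild v moderate |
| 2.0 | 176.8 | 2 | 3 | moderate v severe |
| 2.4 | 212.2 | 3 | 4 | severe on both |
| 2.5 | 221.0 | 3 | 4 | severe on both |

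The other seven values (1.5, 1.6, 1.8, 1.9, 2.1, 2.2 and 2.3) agree. With 88.0 as the factor, the same five values disagree.

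**Step 4: whole µmol/L values**, with the mg/dL equivalent rounded to 0.1. The scales disagree at 121–128, 146–154, 171–181 and 209–225. That is 8 + 9 + 11 + 17 = 45 of the 105 values from 121 to 225 (41 with 88.0). Each disagreement is exactly one grade, higher on the µmol/L scale.

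**Step 5: the BUN row**, at an assumed 0.357 mmol/L per mg/dL. 23 mg/dL is 8.2 and 26 mg/dL is 9.3 mmol/L, against printed Grade 1 limits of 8.3 and 9.5. This row does not convert to within rounding either. At its lower edge it errs in the lenient direction: 23 mg/dL is Grade 1, but 8.2 mmol/L is below the printed start of Grade 1. The calcium row does convert, at a steady 0.25.

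**The case against.** The strongest objection is that the effect depends on a fact that the documents do not show. No passage says that any laboratory reports creatinine in µmol/L, the wording of Protocol 3.2.7 also fits a single laboratory, and two countries do not prove mixed units. This stands: the consequence is conditional, although the mismatch in the table is not.

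A second objection is that Appendix B calls its values guidelines that depend on local parameters. That allows adjustment to a laboratory's normal range, but it does not explain two unequal limits for one grade in one row. The table's attribution to regulatory guidance does not remove the inconsistency either, since the trial has to apply the row as printed.

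A reader might go further in four ways that the documents do not support.

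- **Every creatinine result is over-graded in µmol/L.** Only results in the discordant bands are affected, and a Grade 3 versus 4 difference does not change the recorded severity.
- **Adverse event counts must rise at a µmol/L site.** Protocol 3.12.3 depends on an increase from the earlier grade. A change from 1.4 to 1.6 mg/dL goes from ungraded to Grade 1 in mg/dL, but stays in Grade 1 in µmol/L (123.8 to 141.4). Counts can therefore move either way.
- **A Grade 3 value alone blocks the next cohort.** The conditions in 5.1.5.2 and 5.1.5.3 need an event that is severe, related and due to SYN023. They concern only the 80 LRG subjects, and the NRG review in 5.1.5.4 has no such criterion.
- **The comparison of SYN023 with HRIG is biased.** Both arms at a site would share its unit, and Protocol 2.3 plans for patients to be distributed proportionately between sites. No differential effect is shown.

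**Conclusion.** The mismatch is real and rounding does not explain it. The size of the error does not depend on which scale was intended, and the documents do not settle that question. The result rests on the conversion constant, and its practical effect rests on at least one laboratory reporting in µmol/L. Under that condition, grading becomes inconsistent between laboratories for adverse event reporting, recorded severity and the SAP 9.2 shift tables. The move that matters most is at 2.0 mg/dL (171–181 µmol/L in whole units), where moderate becomes severe. The DSMB advancement conditions are touched only if such an event is also judged related to SYN023. The efficacy endpoints and the sample size are not affected. Minor priority.

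**What to change.** The sponsor should reconcile the two creatinine scales in Appendix B and state which unit governs. SAP 9.2 should say that all creatinine results are converted to that unit and graded centrally, with a stated rounding rule. Creatinine adverse events already graded on the other scale should be re-graded.

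Simply printing converted limits with the gaps closed (133–150, 151–177, 178–221, >221 µmol/L) would presume that the mg/dL scale governs. It would also still disagree with mg/dL rounded to 0.1 at 129–132, 151–154, 178–181 and 222–225 µmol/L, which is 16 whole values. The band 178–181 would again be moderate on one scale and severe on the other. This is why the governing unit and the rounding rule are needed.

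The BUN row should be checked in the same revision. The cost is small: one table row (two if BUN changes), one line of programming, and the re-grading of any events already recorded.
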